influencing and mediating socio-behavioral factors will be explored with questionnaires at 0 and 6 months.

Justification for the study

Young women are a highly vulnerable population in terms of HIV acquisition given 1) limited access to sexual health information and services in many settings [1], 2) limited ability to negotiate condoms in many sexual relationships [2], 3) high risk for HIV acquisition in the setting of gender-based violence which can be very common [3], and 4) the 2-8X increased efficiency of HIV transmission from men-to-women compared to women-to-men [4]. Young women currently account for three-quarters of all new HIV infections in sub-Saharan Africa—a figure that translates to ~7,000 new infections occur per week [5]. Moreover, with the impending youth bulge, the adolescent population will reach >300 million by 2050 [6]. Clearly HIV prevention tools are needed for this population, and PrEP (current recommended as daily oral 300mg tenofovir/200mg emtricitabine) is in many ways an ideal option. It is safe and effective, it can be taken discretely, and it does not require negotiation with sexual partners [7]. And, young women want effective HIV prevention options as evidenced by 86-95% uptake of PrEP in two recent demonstration projects in southern Africa and Kenya [8, 9], as well as numerous advocacy campaigns [10].

Despite the advantages of PrEP, adherence and retention in PrEP programs have been challenging for young women. In two phase III clinical trials of PrEP, plasma tenofovir was detected in only 28-36% of women 18-25 years old [11, 12]. More recently, protective plasma levels of tenofovir were only seen in 38% of young women participating in a demonstration project in South Africa [13]. Additionally, only 10% of young women were still picking up PrEP at 6 months in the above-noted Kenyan demonstration project, despite the high uptake [9]. Novel means to support ongoing use of PrEP and retention in care will be critical to successful HIV prevention efforts in this population.

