The above-noted procedures will be repeated at the Month 3 and Month 6 visit. Additionally, at the Month 6 visit, an RA will collect the following data either in the field or at the study site (within the next two weeks):

- Dried blood spot for tenofovir concentration
- Creatinine (point-of-care)
- Socio-behavioral data (quantitative questionnaire; see Table 1)
- Acceptability data (see below)

Acceptability will be determined quantitatively with the Systems Usability Scale (SUS; [49]). This 10-item Likert scale assesses domains including desired frequency of use, complexity, need for support, functionality, irregularities, ease of learning/use, time required for use, confidence, and training needed. Qualitatively, we will explore *PrEP My Way* in accordance with the Unified Theory of Acceptance and Use of Technology (UTAUT; Figure 5) in up to 20 participants purposively selected to

Figure 5. Unified Theory of Acceptance and Use of Technology

reflect high and low usage of the kits. Questions for each model component are described in Table 3.

All quantitative data will be recorded on encrypted tablets in REDCap. Qualitative interviews will be digitally recorded and transcribed. All data will be collected in a private space using the participant's preferred language (KiSwahili, DhoLuo, or English).

Table 3. Questions to be used in assessing PrEP My Way acceptability	
Model component	Question content
Performance expectancy	Perceived usefulness, personal outcome expectations
Effort expectancy	Perceived effort needed to arrange delivery and use the kit components
Social influence	Perceived norms and stigma
Facilitating conditions	Kit delivery, instructional materials, role of the peer
Behavioral intention to use	Attitudes around current and anticipated future use/non-use
Actual use	DBS tenofovir concentration

Participants will then be disenrolled from the study and linked back to the Lumumba Clinic, Kisumu County Hospital, or a similar clinic of their choice, for continuation of PrEP as desired. A small incentive/thank you gift (worth a minimum of ~500 Kenyan Shilling or \$5 US) will be given at that time for transport and completion of study-related activities (not *PrEP My Way* utilization). The estimated time spent with the participant will be ~2 hours at enrollment, 30 minutes at Months 1 and 3, and ~1 hour at Month 6.

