Control condition. After randomization, a study research assistant (RA) will administer the baseline demographic and socio-behavioral questionnaire. Control participants will then continue to receive PrEP and any other desired sexual health services at Lumumba Clinic or Kisumu County Hospital. The study may provide or assist the clinics in obtaining necessary supplies for routine HIV/STI services in the event of supply chain stock outs. The RA will call the control participant in ~3 months to maintain accurate contact information and remind her that the RA will meet her at her 6-month PrEP appointment in the Lumumba Clinic or Kisumu County Hospital for the final study visit. The RA will make a reminder call one week in advance. If the control participant does not wish to continue PrEP or return to the Lumumba Clinic/Kisumu County Hospital, she may come to the RCTP study site for the final study procedures. The RA will then collect the following using the methods described above:

- Dried blood spot for tenofovir concentration
- Socio-behavioral data (quantitative questionnaire)
- Review of Lumumba Clinic/Kisumu County Hospital chart records for HIV and STI testing and pick up of PrEP and contraception; participants may be asked for clarification if chart records are incomplete

Control participants will then be disenrolled and provided with a small incentive/thank you (worth at least~500 Kenyan Shillings or \$5 US) for completion of study-related activities. They will continue to receive PrEP and other sexual health services at Lumumba Clinic, Kisumu County Hospital, or another clinic as desired.

Peer identification and hiring, and oversight. Peers will not be participants. They will be identified from PrEP programs in the Kisumu region. Peers will be 18-30 years old women who have themselves taken PrEP for at least 3 months and are fluent in KiSwahili, DhoLuo, and/or English. If they do not own a smart phone, the study will provide one for showing the *PrEP My Way* video guidance and enabling two-way communication with participants (e.g., SMS, WhatsApp). Although already experienced with PrEP, all peers will be trained about PrEP using Kenyan national guideline materials [35]. They will also undergo sensitivity training, including

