Feasibility. Feasibility will be assessed by the following metrics: 1) receipt of the *PrEP My Way* kit at Months 1, 3, and 6, and 2) ability of the participant to use each aspect of the kit (i.e., the HIV self-test, use of the vaginal swab, and self-administration of medroxyprogesterone [if desired]) per protocol. The intervention will be considered feasible if $\geq 70\%$ (35/50) participants 1) receive a kit and 2) achieve a readable HIV test, usable vaginal swab, and self-injection of medroxyprogesterone, if desired, at $\geq 66\%$ (2/3) of visits.

Acceptability. The *PrEP My Way* intervention will be considered acceptable if $>70\%$ (35/50) participants rate 70% (7/10) items on the SUS as "very good" or higher. The qualitative interview will delve deeply into each of the four domains of the UTAUT model to provide in depth feedback on the intervention.

Primary outcomes- Preliminary impact on PrEP adherence and program retention at 6 months. PrEP adherence will be assessed primarily by DBS for tenofovir diphosphate (TFV-DP) concentration. The TFV-DP concentration will provide an estimate of doses taken over the prior 3 months (see Table 4; [11, 50]). Retention will be assessed by kit receipt in the intervention arm and clinic attendance per clinic records in the control arm at Month 6. Potential influencing and mediating socio-behavioral factors (Table 2) will be explored.

Secondary outcomes. We will assess the following:

Table 4. TFV-DP concentrations in DBS	
Estimated use	Median fmol/punch (IQR)

- Self-reported PrEP adherence at Months 1, 3, and 6 (intervention arm) and Month 6 (control arm). We will use the 3-item scale developed by Wilson et al, which involves different recall tasks (frequency, percent, and rating of adherence) over the prior 30 days [51]
- PrEP persistence over the 6-month period
- Rates of STI testing at Months 1, 3, and 6
- Rates of pregnancy test and contraception pick up at Months 1, 3, and 6
- Cost estimates

Protective*	>1,250
Moderate	900-1,249
Low	<900

*Exact value to be explored (see text)

Analysis

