Our power calculations are based on 80 participants, given an expected loss to follow-up of 20% (estimated from our current MPYA study). As shown in Figure 6, assuming a standard deviation of 10%, 80 participants will have limited power to detect a difference of 20% between the study arms (e.g., ~40% power if the primary outcome is seen in 40% of the control group versus 60% in the intervention group; see the circled green dot). If a stronger effect is seen (e.g., closer to the ideal target of 40%), we may achieve >80% power. We believe this sample size is appropriate for the development of the *PrEP My Way* intervention. If the intervention is also found to be feasible and acceptable, we look forward to fully testing the intervention in a subsequent, fully powered study.

[figure not shown]
Participant retention and withdrawal

Participants will be tracked primarily through peers (intervention) and the clinic visits (standard of care). Individuals missing scheduled appointments will be contacted through study retention teams. Participants will be able to withdraw from the study at any time.

Ethical Considerations

Human subjects

Figure 6. Estimate power for the study sample size

This study will involve young Kenyan women in two sets of study procedures to develop and preliminarily test the *PrEP My Way* intervention.

- Intervention development (Aim 1). We will use a client-centered approach, involving individual interviews and two focus group discussions with up to 25 Kenyan women to optimally design the *PrEP My Way* kit (with instructional materials) and peer delivery system (including communication and kit delivery plans).
- Pilot randomized controlled trial (Aim 2). We will randomize 150 Kenyan women to *PrEP My Way* versus standard of care (i.e., clinic-based delivery of PrEP and sexual health services) and follow them for 6 months. These participants will be distinct from those participating in the intervention development aspects of the study. Feasibility will be assessed by receipt of the kit at 1, 3, and 6 months and ability to use its components per protocol. Acceptability will be determined through a mixed-methods interview at 6 months. Preliminary impact will be evaluated by dried blood spot tenofovir levels (adherence) and kit use/clinic attendance at 6 months (retention) as primary outcomes. Mediators and moderators of PrEP use (e.g., empowerment and mental health) will be explored through questionnaires at baseline and 6 months.

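### Holding the control arm's final study visit at the Month 6 PrEP appointment may raise control retention, a primary outcome, and shrink the difference between arms

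*Combined protocol and SAP*

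**What the plan says.** Program retention at Month 6 is one of the two primary outcomes of the combined protocol and SAP. Under Outcome measures, Primary outcomes: "Retention will be assessed by kit receipt in the intervention arm and clinic attendance per clinic records in the control arm at Month 6". The arms are compared by chi-square test (Analysis, Primary outcomes).

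The Control condition paragraph (Aim 2, Study procedures) describes the study's contact with control women. A research assistant (RA) phones at about 3 months to check contact details and announces where the study will end: "the RA will meet her at her 6-month PrEP appointment in the Lumumba Clinic or Kisumu County Hospital for the final study visit". A second call follows a week beforehand. At that visit the RA takes the dried blood spot (DBS) and the questionnaire and reviews the chart, including PrEP pick-up. The woman then receives an incentive of at least about 500 KSh for her study activities. A woman who does not want to stay on PrEP or go back to the clinic can have the final procedures done at the RCTP study site.

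Participant retention and withdrawal adds: "Individuals missing scheduled appointments will be contacted through study retention teams".

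In the intervention arm (Intervention condition), the peer makes contact a week before each kit visit. The RA's Month 6 data may be taken in the field or at the study site, up to two weeks later. The incentive has the same minimum and is expressly not tied to kit use. The randomization paragraph describes the control arm simply as ordinary follow-up at the two facilities.

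**The concern.** In the control arm, the occasion at which the study collects its data is, by default, also the event scored as the outcome. Two study calls direct the woman to that event. Attendance prompted by the study and attendance for PrEP appear the same in an attendance record, and the retention definition has no rule to separate them. PrEP pick-up is taken from the chart but is not part of that definition.

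The trial is motivated by steep drop-off under clinic care. The Justification section reports that "only 10% of young women were still picking up PrEP at 6 months" in a Kenyan demonstration project. If study contact raises control attendance, the trial understates that drop-off and may miss part of a real benefit of the kit. The follow-on trial would then be planned on a control rate that is too high.

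**Working it through.** **1. The two arms at Month 6**

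| | Intervention | Control |
|---|---|---|
| Scored event | Kit receipt | Clinic attendance in clinic records |
| Prompt before it | Peer contact one week ahead, part of the intervention | RA calls at about 3 months and one week ahead, not described as usual care |
| RA data collection | Field or study site, up to two weeks later | At the PrEP appointment by default; RCTP for women who do not want to continue PrEP or return |
| Incentive | For study activities | For study activities |

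The asymmetry lies in the second and third rows. Intervention data collection can be separate from the scored event. Control data collection, by default, is not.

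**2. The plan's own power figure**

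The Power section gives about 40% power for 40% versus 60% with 80 participants. It is based on PrEP adherence, not retention. Taking 40 per arm and two-sided alpha 0.05 (assumed; none is stated), the pooled normal approximation is

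Φ{[0.20 − 1.96 × √(2 × 0.5 × 0.5/40)] / √[(0.4 × 0.6 + 0.6 × 0.4)/40]} = Φ{(0.20 − 0.219)/0.110} = 43%.

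Exact enumeration gives 46% for the Pearson chi-square and 37% for the Yates and Fisher tests. These bracket the stated figure, so it is not disputed here.

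**3. Illustration with an assumed prompting effect**

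Let c be true control retention, t true intervention retention, and f the share of would-be control non-attenders whom study contact brings to the clinic. The documents give no value for f. The 40% and 60% are borrowed from the adherence example because the plan states no retention assumption.

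Observed control retention = c + f(1 − c). With c = 40%, t = 60% and 40 per arm:

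| f | Only control affected | Difference | Power | Both arms affected equally | Difference | Power |
|---|---|---|---|---|---|---|
| 0 | 40% vs 60% | 20 points | 43% | 40% vs 60% | 20 points | 43% |
| 10% | 40 + 0.1 × 60 = 46% vs 60% | 14 points | 24% | 46% vs 64% | 18 points | 36% |
| 20% | 40 + 0.2 × 60 = 52% vs 60% | 8 points | 11% | 52% vs 68% | 16 points | 31% |

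When both arms are affected, the difference is (t − c)(1 − f). The change in the difference does not depend on sample size. With 60 per arm (150 randomized, 20% lost), the control-only power falls from 59% to 33% and 14%.

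**4. Two variations**

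- If only the 80% expected to be followed can be prompted, and f is the share of lapsed women within that group, observed control retention is c + f(80% − c). At f = 10% this is 40 + 0.1 × 40 = 44% (16 points); at f = 20% it is 48% (12 points).
- If true control retention were the 10% pick-up cited in the Justification, then f = 10% gives 10 + 0.1 × 90 = 19%, and f = 20% gives 28%. Where drop-off is steep, a small prompting effect can nearly double the apparent usual-care rate.

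**The case against.** Several points on the other side stand, and they limit the claim.

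- **The RCTP route.** Women who do not want to continue PrEP or return to the clinic can finish the study elsewhere. They are many of the women whom a prompt might otherwise bring back, so f may be small. The route does not cover a woman who has lapsed but is undecided; the default script directs her to the clinic.
- **The incentive.** A reader might infer that the study pays control women to attend the clinic. The text does not support this: the payment is for study activities and can be had at RCTP. It is merely handed over at the clinic visit by default.
- **Tracing.** The sentence on missed appointments may mean study visits only. Reading it as pursuit of missed clinic PrEP appointments is an inference.
- **Shared features.** The incentive and tracing apply in both arms, and the intervention arm also has a one-week contact. Peer contact belongs to the intervention, whereas RA calls are not described as part of usual care, so the problem is only partly shared.
- **Clinic records.** Retention is already to be scored from records, and PrEP pick-up is already abstracted. What is missing is a fixed window and a rule that counts PrEP service rather than presence.
- **Purpose.** This is a pilot with acknowledged limited power. The DBS outcome reflects doses over the prior 3 months and is not defined by attendance. A bias confined to the control arm runs toward no difference, so it would not create an apparent benefit.

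**Conclusion.** The plan as written can raise control retention through the study's own contact, and the retention definition cannot separate prompted from unprompted attendance. If the effect falls mainly on the control arm, the usual-care drop-off is understated and the difference is biased toward zero. The illustrative losses (20 points falling to 14 or 8) rest on an assumed f, on adherence figures used in place of retention, and on an unaffected intervention arm. They show sensitivity and are not estimates.

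Two stronger readings are not supported. One is that control retention tells us nothing about usual care: the RCTP route and the unknown size of the effect allow only that it may understate the drop-off. The other is that the planned difference is wiped out: in this illustration that needs a third of would-be non-attenders brought in (40 + 60/3 = 60%), or half under the 80% cap (40 + 0.5 × 40 = 60%), with no effect in the other arm. Nothing in the documents supports either value.

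This should be fixed before Month 6 visits begin, because prompted attendance cannot be identified afterwards. It does not undermine the trial as a whole.

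**What to change.** 1. Define control retention as a clinic-recorded PrEP visit or refill within a fixed, stated Month 6 window, using the chart review already planned.
2. Hold the control final study visit, with its incentive, at RCTP or in the field, apart from the PrEP appointment. RCTP is already allowed for some control women. It is next door to Lumumba Clinic, and Kisumu County Hospital is a 5-minute drive from the study offices.
3. In the control arm, limit RA calls and retention-team contact to the study visit and contact details, with no prompt about the clinic PrEP appointment. State in Participant retention and withdrawal which appointments are traced. Contact for safety or test results is unaffected.
4. Apply the same Month 6 timing rule for DBS in both arms. Delaying control calls until the retention window has closed would make control samples later than intervention samples and disturb the adherence comparison.
5. As support, report control clinic attendance or refill at Month 1, which precedes both scheduled RA calls. Early retention is already among the secondary analyses.

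The cost is protocol wording and RA scheduling. A separate visit may lose a few control DBS samples and questionnaires. Some prompting may remain, since any study call reminds a woman of PrEP, but the study would no longer direct her to the scored event.

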Recruitment. We will identify young women to participate in the pilot RCT at the time they initiate PrEP at the Lumumba Clinic or Kisumu County Hospital. Participants may also be identified in the nearby community and invited to attend either facility to initiate PrEP and enroll in the study. Community recruitment will be done in areas such as hotspots, fish landing points, and within the general low end estates with the help of community health volunteers. These participants will be distinct from those engaged in the development of the intervention (Aim 1) to increase likelihood of generalizable findings. Similar to Aim 1, participants will be approached randomly (e.g., the second client seen on a given day) with stratification by age (16-20 versus 20-24). Only up to three participant will be enrolled per site per day to avoid clustering effects, as young women often present for PrEP services in groups [40].

Figure 4. Participant flow for the pilot RCT of *PrEP My Way* versus standard of care

Consent, enrollment, and randomization. Eligibility criteria for the pilot RCT participants are as follows. All participants will have started PrEP within the past two weeks:

- Inclusion criteria
 - Young woman (age 16-24 years); we will enroll emancipated minors (e.g., those who have not yet attained the age of legal competency as defined by state law, but who are entitled to treatment as if they had by virtue of assuming adult responsibilities, such as self-support, marriage, or procreation) per Kenyan national guidelines [39] or 16-17 year-olds with parental/caregiver consent
 - Initiating PrEP (this criterion subsumes all necessary safety assessments for starting PrEP, including HIV-negative status, normal renal function, and lack of Hepatitis B infection)
 - Reported sexual activity in the past 3 months
 - Residence in the Kisumu region (maximum of 20 km from our study offices at RCTP)
 - Phone ownership
 - Ability to understand KiSwahili, DhoLuo, and/or English

- Exclusion criteria- inability to provide informed consent (e.g., intoxication, mental disability)

Note: Participants may also be excluded at the discretion of the principal investigator (e.g., because of co-enrollment with a study that would compromise study aims or disruptive behavior).

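### Month 6 dried blood spot collection options differ by arm, and for controls the route turns on continuing PrEP or returning to the clinic, which risks outcome-related missing data in a primary outcome

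*Combined protocol and SAP*

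**What the plan says.** The adherence primary outcome is the tenofovir diphosphate (TFV-DP) concentration in a DBS at 6 months, compared between arms as protective or not by a chi-square test (Outcome measures; Analysis, Primary outcomes).

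- **Intervention arm** (Intervention condition): for Month 6 the text reads: "an RA will collect the following data either in the field or at the study site (within the next two weeks"). The DBS heads the list.
- **Control arm, default** (Control condition): the participant is told by phone that "the RA will meet her at her 6-month PrEP appointment in the Lumumba Clinic or Kisumu County Hospital for the final study visit".
- **Control arm, alternative**: "If the control participant does not wish to continue PrEP or return to the Lumumba Clinic/Kisumu County Hospital", then "she may come to the RCTP study site for the final study procedures". The next sentence adds: "The RA will then collect the following using the methods described above".
- **Tracking** (Participant retention and withdrawal): "Participants will be tracked primarily through peers (intervention) and the clinic visits (standard of care"). Retention teams contact anyone who misses an appointment.
- **Table 1**: the Month 6 DBS cell reads RA in both arms, with no place given.
- **Analysis**: intention-to-treat is named for the primary outcomes, with a per-protocol analysis as well. Nothing says how a woman without a DBS result is counted.

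**The concern.** In the control arm, the ease of giving a sample follows PrEP continuation and clinic return. Both are close to the two primary outcomes, TFV-DP and clinic attendance at Month 6. In the intervention arm the RA may go to the woman.

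The group affected may be large. The Power section expects adherence to fall by 60% between enrollment and Month 6, and the Justification cites a Kenyan project in which 10% of young women were still collecting PrEP at 6 months. The Justification also names transport costs and clinic hours as major obstacles to staying on PrEP.

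If controls who have stopped are sampled less often than intervention women who have stopped, the control proportion with protective levels among those sampled is too high. The intervention effect then looks too small. A sample not taken at Month 6 cannot be recovered at analysis, so the collection rule matters separately from the handling of missing values.

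**Working it through.** **The plan's own figures.** The Power section uses 80 analysable women after 20% loss, rates of 40% (control) and 60% (intervention), and about 40% power. 80/(1 - 0.20) = 100, or 50 per arm. With 40 per arm and an assumed two-sided 5% level (the plan states none), power is 43.1% by the pooled chi-square formula and 36.9% by Fisher's exact test. These bracket the stated figure, so it serves as a reference. The current text randomizes up to 150, or 75 per arm.

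**Formula.** Let p be the true proportion protective, a the probability of obtaining a DBS from a protective woman, and b the same for a non-protective woman.

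- Complete-case proportion = p·a / (p·a + (1 - p)·b)
- Proportion with missing counted as non-protective = p·a

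The documents give neither a nor b. All capture rates below are assumptions.

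**No true difference, p = 0.40 in both arms.**

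- Controls, a = 0.90, b = 0.70: 0.36/(0.36 + 0.42) = 0.36/0.78 = 46.2%. Total control loss is 22%, close to the planned 20%.
- Intervention capture unrelated to adherence: 40%. False deficit: 6.2 points.
- Intervention capture also related to adherence, a = 0.95, b = 0.80: 0.38/(0.38 + 0.48) = 0.38/0.86 = 44.2%. False deficit: 46.2 - 44.2 = 2.0 points.
- Same a and b in both arms: no deficit.

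**Planned difference, 40% versus 60%.** Intervention capture is 95% throughout and control a = 0.95, so p·a = 0.38 for controls. Power is for the complete-case comparison.

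| Control b | Control loss | Control rate seen | Difference seen | Power, 50 per arm | Power, 75 per arm |
|---|---|---|---|---|---|
| 95% | 5% | 40.0% | 20.0 | 50% | 67% |
| 80% | 14% | 44.2% | 15.8 | 32% | 45% |
| 70% | 20% | 47.5% | 12.5 | 21% | 30% |
| 50% | 32% | 55.9% | 4.1 | 6% | 7% |

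The last row loses more controls than the plan expects. The 70% row matches the planned 20% loss in that arm.

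**Missing counted as non-protective.** In every row the rates become 0.40 × 0.95 = 38% and 0.60 × 0.95 = 57%, a difference of 19 points, because b drops out. Power is 48% (50 per arm) or 65% (75 per arm). The rule fails only if protective women are captured unequally. With p = 0.40 in both arms, a = 0.80 in the intervention arm and a = 0.95 in controls, the rates are 32% and 38%, a false deficit of 6 points.

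**The case against.** The strongest reply is that the plan does provide for controls who have stopped. They have a written route, a contact call at about 3 months, a further call ("The RA will make a reminder call one week in advance"), an incentive of at least about 500 Kenyan shillings, and retention-team contact after a missed appointment. A reader might infer that a control gets a result only if she is still on PrEP. The text does not say that; the link to PrEP status is a plausible inference.

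A reader might also infer an added journey of up to 20 km. That figure is an eligibility limit on residence ("maximum of 20 km from our study offices at RCTP"). The study site is next door to Lumumba Clinic, and Kisumu County Hospital is a five-minute drive from the study offices. The trip is about as long as the one to the PrEP clinic. What differs is that it is a separate, optional visit without a PrEP pick-up.

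The intervention arm is not free of the problem. Its DBS is tied to the Month 6 kit visit, and no route is written for a woman who declines the kit. This weakens any firm claim about the size of the bias and leaves its direction probable only.

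It can also be said that Table 1 and the reference back to the methods above already give controls the field option. Neither does so clearly: the table names who collects and not where, and the reference back follows a sentence that has just set the place. This may be a gap in wording rather than intent, but staff will work from the wording.

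Finally, this is a pilot. At 40 per arm the standard error of the difference is about sqrt(2 × 0.24/40) = 11 points, so a bias of a few points lies within sampling noise. That limits the weight of the point, but the correction is cheap.

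**Conclusion.** The point stands as a risk created by unequal written collection rules for a primary outcome. It does not show that a control's result is conditional on being on PrEP.

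The size is unknown. One illustration, with control capture of 90% and 70% and intervention capture unrelated to adherence, moves a true 40% to 46%. The false deficit falls to about 2 points if intervention capture is 95% and 80%, and to zero if the patterns match. The direction, against the intervention, rests on non-continuing controls being sampled less often than non-continuing intervention women.

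The bias arises in a complete-case analysis, which the plan neither adopts nor excludes. It would be wrong to conclude that counting missing samples as non-protective cannot help: that rule removes bias from unequal capture of non-protective women, provided protective women are captured equally in both arms. The plan does not specify the rule, and unequal collection makes its condition less secure.

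**What to change.** In the Intervention condition and Control condition sections, state one rule for both arms, independent of PrEP status and of kit acceptance:

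- The RA collects the DBS and questionnaire at the study site or in the field at a place the woman chooses, within the same window in both arms.
- The field option is expressly offered to any woman in either arm who has stopped PrEP or misses the Month 6 visit.
- The place of collection is recorded.

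In the Analysis section, report DBS completeness by arm and by retained or not retained. Add a sensitivity analysis counting a missing DBS as non-protective, and state its condition of equal capture of protective women in both arms.

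The cost is protocol wording and some additional RA travel to control women, within the 20 km residence limit. RA field collection is already planned for the intervention arm. The change needs to be in place before Month 6 visits begin.
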